8.3.5.1. Exposure During Pregnancy

Details of all pregnancies in female partners of male participants will be collected after the start of study intervention and until the last follow-up visit.

If a pregnancy is reported, the investigator should inform the sponsor within 24 hours of learning of the pregnancy and should follow the procedures outlined in [Appendix 4](#).

Abnormal pregnancy outcomes (eg, spontaneous abortion, fetal death, stillbirth, congenital anomalies, ectopic pregnancy) are considered SAEs.

8.3.5.2. Exposure During Breastfeeding

Scenarios of exposure during breastfeeding must be reported, irrespective of the presence of an associated SAE, to Pfizer Safety within 24 hours of the investigator's awareness, using the CT SAE Report Form. An exposure during breastfeeding report is not created when a Pfizer drug specifically approved for use in breastfeeding women (eg, vitamins) is administered in accord with authorized use. However, if the infant experiences an SAE associated with such a drug's administration, the SAE is reported together with the exposure during breastfeeding.

8.3.5.3. Occupational Exposure

An occupational exposure occurs when, during the performance of job duties, a person (whether a healthcare professional or otherwise) gets in unplanned direct contact with the product, which may or may not lead to the occurrence of an AE.

An occupational exposure is reported to Pfizer Safety within 24 hours of the investigator's awareness, using the CT SAE Report Form, regardless of whether there is an associated SAE. Since the information does not pertain to a participant enrolled in the study, the information is not recorded on a CRF; however, a copy of the completed CT SAE Report Form is maintained in the investigator site file.

8.3.6. Medication Errors

Medication errors may result from the administration or consumption of the investigational product by the wrong participant, or at the wrong time, or at the wrong dosage strength.

Exposures to the investigational product under study may occur in clinical trial settings, such as medication errors.

Safety Event	Recorded on the CRF	Reported on the CT SAE Report Form to Pfizer Safety Within 24 Hours of Awareness
Medication errors	All (regardless of whether associated with an AE)	Only if associated with an SAE

Medication errors include:

- Medication errors involving participant exposure to the investigational product;
- Potential medication errors or uses outside of what is foreseen in the protocol that do or do not involve the study participant.

Such medication errors occurring to a study participant are to be captured on the medication error page of the CRF, which is a specific version of the AE page.

In the event of a medication dosing error, the sponsor should be notified immediately.

Whether or not the medication error is accompanied by an AE, as determined by the investigator, the medication error is recorded on the medication error page of the CRF and, if applicable, any associated AE(s), serious and nonserious, are recorded on an AE page of the CRF.

Medication errors should be reported to Pfizer Safety within 24 hours on a CT SAE Report Form **only when associated with an SAE**.

8.4. Treatment of Overdose

For this study, any dose of PF-07081532 greater than that projected to result in exposures greater than the defined PK stopping limit CCI

within a 24-hour time period will be considered an overdose.

In the event of an overdose, the investigator/treating physician should:

1. Contact the medical monitor immediately.
2. Closely monitor the participant for any AEs/SAEs and laboratory abnormalities until PF-07081532 can no longer be detected systemically (at least 5 days).
3. Document the quantity of the excess dose as well as the duration of the overdose in the CRF.

4. Overdose is reportable to Safety **only when associated with an SAE**.
5. Obtain a blood sample for PK analysis within 3 days from the date of the last dose of study intervention if requested by the medical monitor (determined on a case-by-case basis).

Decisions regarding dose interruptions or modifications will be made by the investigator in consultation with the medical monitor based on the clinical evaluation of the participant.

8.5. Pharmacokinetics

8.5.1. Plasma for Analysis of PF-07081532

Blood samples of approximately 3 mL, to provide approximately 1 mL of plasma, will be collected into appropriately labeled tubes containing dipotassium ethylenediaminetetraacetic acid (K₂EDTA) for measurement of plasma concentrations of PF-07081532 at times specified in the [Schedule of Activities](#). Instructions for the collection and handling of biological samples will be provided in the laboratory manual or by the sponsor. The actual date and time (24-hour clock time) of each sample will be recorded.

The actual times may change, but the number of samples will remain the same. Any changes in the timing or addition of time points for any planned study assessments must be documented and approved by the relevant study team member and then archived in the sponsor and site study files but will not constitute a protocol amendment.

Samples will be used to evaluate the PK of PF-07081532. Samples collected for measurement of plasma concentrations of PF-07081532 will be analyzed using a validated analytical method in compliance with applicable standard operating procedures (SOPs).

CCI

The PK samples must be processed and shipped as indicated in the instructions provided to the investigator site to maintain sample integrity. Any deviations from the PK sample handling procedure (eg, sample collection and processing steps, interim storage or shipping conditions), including any actions taken, must be documented and reported to the sponsor. On a case-by-case basis, the sponsor may decide as to whether sample integrity has been compromised.

Drug concentration information that may unblind the study will not be reported to investigator sites or blinded personnel until the study has been unblinded.

CCI

8.5.3. Urine for Analysis of PF-07081532

[figure not shown]
[figure not shown]
Urine will be collected at times specified in the [Schedule of Activities](#).

- **Prior to dosing on Day 1**, each participant must complete a forced void with an **aliquot** (approximately 10 mL) from this urine (urine blank) labeled and stored frozen for measurement of drug concentrations, per detailed instructions offered in a laboratory manual prior to the start of the study.
- **Following dosing** on Days Specified in the **Schedule of Activities**, each void post dose will be collected and saved in a container and stored in refrigerated conditions (ie, 2-8°C) for the duration of the collection intervals, as specified in the **Schedule of Activities**.
 - Just prior to the first collection interval, participants will complete a forced void and the urine will be discarded;
 - At the end of each collection interval, participants must complete a forced void with this complete void included as part of the interval collection;
 - The urine container will be mixed thoroughly and total volume plus weight of the urine collected during the interval recorded;
 - An **aliquot** (approximately 20 mL) will be labeled and stored frozen for the potential measurement of drug concentrations **CCI** [REDACTED] per detailed instructions offered in a laboratory manual prior to the start of the study; and the remaining urine discarded.

[figure not shown]
[figure not shown]
Details regarding the processing, storage and shipping of the samples will be provided in the lab manual. The shipment address and assay lab contact information will be provided to the investigator site prior to initiation of the study. The urine samples must be processed as indicated to maintain sample integrity. Any deviations from the urine sample processing steps given in the protocol or lab manual, including any actions taken, must be documented and reported to the sponsor. On a case-by-case basis, the sponsor may make a determination as to whether sample integrity has been compromised. Any sample deemed outside of

established stability, or of questionable integrity, will be considered a protocol deviation. Samples for analysis of PF-07081532 PK will be analyzed using validated analytical methods in compliance with Pfizer standard operating procedures.

CCI

CCI

CCI

8.6.3. Body Weight

Body weight measurements will be obtained at the time points outlined in the [Schedule of Activities](#). If possible, the same scale should be used for a particular participant for all body weight measurements obtained at the CRU. For measuring weight, a scale with appropriate range and resolution is used and must be placed on a stable, flat surface.

[figure not shown]
Body weight will be measured at outpatient visits to the study site as listed in the [Schedule of Activities](#) under the following conditions:

- After void of urine;
- After removal of shoes, bulky layers of clothing, and jackets so that only light clothing remains;
- While remaining still during measurement.

During admission to the CRU, body weight will be measured at the time points listed in the [Schedule of Activities](#). Measurement will be taken under the following conditions:

- In the morning, prior to eating and drinking and prior to dose administration, where applicable;
- After the participant has been asked to void;
- While wearing only a hospital gown and no shoes;
- While remaining still during measurement.

CCI

CCI

CCI

8.9. Health Economics

Health economics/medical resource utilization and health economics parameters are not evaluated in this study.

9. STATISTICAL CONSIDERATIONS

Detailed methodology for summary and statistical analyses of the data collected in this study is outlined here and further detailed in a statistical analysis plan (SAP), which will be maintained by the sponsor. The SAP may modify what is outlined in the protocol where appropriate; however, any major modifications of the primary endpoint definitions or their analyses will also be reflected in a protocol amendment.

9.1. Statistical Hypotheses

No formal statistical hypothesis testing will be performed in this study.

9.2. Sample Size Determination

Part A and Part C (if conducted), participants with T2DM: a sample size of up to approximately 10 participants per cohort (8 active, 2 placebo) has been selected to minimize exposure to humans to a new chemical entity while allowing adequate characterization of safety and tolerability, PK, CCI at each dose level in this population.

Part B (if conducted), obese participants: a sample size of up to approximately 15 participants per cohort (12 active, 3 placebo) has been selected to minimize exposure of humans to a new chemical entity while allowing adequate characterization of safety and tolerability, PK, CCI at each dose level in this population. CCI

CCI				

CCI

CCI

9.3. Populations for Analysis

For purposes of analyses the following populations are defined:

Table 10. Populations for Analysis

Population	Description
Enrolled	All participants who sign the ICD.
Randomly assigned to investigational product	All participants randomly assigned to investigational product regardless of whether or not the investigational product was administered.
Evaluable	All participants randomly assigned to investigational product and who take at least 1 dose of investigational product. Participants will be analyzed according to the product they actually received.
Safety	All participants randomly assigned to investigational product and who take at least 1 dose of investigational product. Participants will be analyzed according to the product they actually received.
PK Concentration Set	The PK concentration population is defined as all randomized participants who received at least 1 dose of PF-07081532 and in whom at least 1 plasma concentration value is reported.
PK Parameter Set	The PK parameter population is defined as all randomized participants that received at least 1 dose of PF-07081532 and have at least 1 of the PK parameters of interest calculated.
CCI	[REDACTED]

9.4. Statistical Analyses

9.4.1. Efficacy Analyses

An efficacy analysis is not applicable to this study.

9.4.2. Safety Analyses

All participants who received at least 1 dose of study medication will be included in the safety analyses and listings. AEs, ECGs, BP, pulse rate, and safety laboratory data will be reviewed and summarized on an ongoing basis during the study to evaluate the safety of participants. Any clinical laboratory, ECG, BP, and pulse rate abnormalities of potential clinical concern will be described. Safety data will be presented in tabular and/or graphical format and summarized descriptively, where appropriate.

Medical history and physical examination information, as applicable, collected during the course of the study will be considered source data and will not be required to be reported, unless otherwise noted. However, any untoward findings identified on physical and/or neurological examinations conducted during the active collection period will be captured as AEs, if those findings meet the definition of an AE.

Data collected at screening that are used for inclusion/exclusion criteria, such as laboratory data (unless noted below), ECGs, and vital signs, will be considered source data, and will not be required to be reported, unless otherwise noted. Demographic data collected at screening will be reported. In addition, selected screening laboratory data: CCI [REDACTED]
TBA CCI [REDACTED] will be reported.

9.4.2.1. Electrocardiogram Analyses

Changes from baseline for the ECG parameters QT interval, heart rate, QTcF interval, PR interval, and QRS interval will be summarized by treatment and time.

The number (%) of participants with maximum postdose QTcF values and maximum increases from baseline in the following categories will be tabulated by treatment:

Safety QTcF Assessment

Prolongation	Mild	Moderate	Severe
Absolute value (msec)	>450-480	>480-500	>500
Increase from baseline in QTcF (msec)		30-60	>60

In addition, the number of participants with corrected and uncorrected QT values >500 msec will be summarized.

At the nominal time points, the mean of the triplicate measurements will be used to represent a single observation at that time point. If any of the 3 individual ECG tracings has a QTcF value >500 msec, but the mean of the triplicates is not >500 msec, the data from the participant's individual tracing will be described in a safety section of the study report in order to place the >500 msec value in appropriate clinical context. However, values from individual tracings within triplicate measurements that are >500 msec will not be included in the categorical analysis unless the average from the triplicate measurements is also >500 msec.

In addition, an attempt will be made to explore and characterize the relationship between plasma concentration and QT interval length using a PK^{CC1} modeling approach. The results of such analyses will not be included in the CSR.

9.4.3. Pharmacokinetic Analyses

9.4.3.1. PF-07081532 Pharmacokinetics

The populations for PK concentration and PK parameter analyses are defined in [Table 10](#).

PK parameters for PF-07081532 following multiple dose administration will be derived from the concentration-time profiles using non-compartmental methods as data permit. The PK parameters to be assessed in this study, their definition, and method of determination are outlined in [Table 11](#) and [Table 12](#). In all cases, actual PK sampling times will be used in the derivation of PK parameters. PK samples from placebo samples will not be routinely analyzed. Additional detail on PK parameter definition for titrated and non-titrated cohorts will be provided in the SAP.

Table 11. Definition of Plasma PK Parameters for PF-087081532

Parameter	Day 1 (D1) or Steady State (SS)	Definition	Method of Determination
C_{\max}	D1 & SS	Maximum plasma concentration observed from time zero to 24 hours	Observed directly from data
T_{\max}	D1 & SS	Time for C_{\max}	Observed directly from data as time of first occurrence
C_{\max} (dn)	D1 & SS	C_{\max} normalized to a 1 mg dose	C_{\max} /Dose
AUC_{24}	D1 & SS	Area under the plasma concentration-time profile from time zero to time 24 hours	Linear/Log trapezoidal method
AUC_{24} (dn)	D1 & SS	AUC_{24} normalized to a 1 mg dose	AUC_{24} /Dose
$t_{1/2}^a$	SS	Terminal half-life	$\log_2(2)/k_{el}$, where k_{el} is the terminal phase rate constant calculated by a linear regression of the log-linear concentration-time curve. Only those data points judged to describe the terminal log-linear decline will be used in the regression.

a. If data permit.

Table 12. Definition of Urine PK Parameters for PF-087081532

Parameter	Steady State (SS)	Definition	Method of Determination
Ae ₂₄	SS	Amount of unchanged drug recovered in urine over 24 hours	Sum of [urine concentration* sample volume ^a] for each collection over the dosing interval
Ae ₂₄ %	SS	Percent of dose recovered in urine as unchanged drug	100* Ae ₂₄ /Dose
CL _r	SS	Renal clearance	Ae ₂₄ /AUC ₂₄

a. sample volume = (Urine weight in g/1.020), where 1.020 g/mL is the approximate specific gravity of urine.

[figure not shown]
[figure not shown]
[figure not shown]
The plasma and urine PK parameters will be summarized descriptively by actual dose received (and treatment, if applicable), in accordance with Pfizer standards. Each Cohort will be considered as a separate treatment. If data permit, dose-normalized area under the plasma concentration time profile from time 0 to 24hr [AUC₂₄ (dn)] and dose-normalized C_{max} [C_{max} (dn)] will be plotted against dose (potentially on a logarithmic scale depending on the extent of the dose range) (and treatment, if applicable), and will include individual participant values and the geometric means for each dose (and treatment, if applicable). These plots will be used to help understand the relationship between the PK parameters and dose (and treatment, if applicable).

Plasma concentrations of PF-07081532 will be listed and descriptively summarized by nominal PK sampling time and dose (and treatment, if applicable). Individual participant and median profiles of the plasma concentration-time data will be plotted by dose (and treatment, if applicable) using actual and nominal times, respectively. Median profiles will be presented on both linear-linear and log-linear scales.

CCI

[figure not shown]
[figure not shown]
CCI

CCI

PFIZER CONFIDENTIAL

CCI

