4.3.4. Dose Range and Margins

The planned dose range for this study (10-300 mg QD, but with the potential to escalate up to 1000 mg QD depending upon observations at lower doses) was chosen in order to appropriately bracket the projected efficacious dose to cover the potential impact of uncertainty in projection of efficacious concentration or of unanticipated factors on drug exposure, while accommodating feasibility considerations. **CCI**

Predicted exposure levels and safety margins for a range of anticipated doses for this study are provided in [Table 8](#) below. All exposure-based safety margins were calculated using unbound concentrations. This table gives an overview of the potential dose levels; however, doses may be adjusted as long as the the projected increment of C_{max} and AUC_{24} between dose levels is no greater than approximately 3.3-fold and the projected exposure is not expected to exceed the PK stopping limits.

It is anticipated that dose titration will be required in this study; details are provided in [Section 4.3.5](#).

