- If, at any dose level, the average exposure reaches or exceeds the pharmacokinetic (PK) stopping limits of:
 - [REDACTED]
 - [REDACTED]

These stopping limits are based on the unbound exposures at the NOAEL in the non-human primate (NHP) toxicity study (see [Section 2.2.3](#)) after accounting for protein binding in humans.

- If, based on the observed data, the group mean maximum observed concentration (C_{max}) or area under the curve (AUC) (based on total plasma concentration) of the next planned dose is projected to exceed the escalation limits, that dose will not be explored. Modified doses may be explored if they are not expected to exceed PK stopping criteria.

Progression to the next dose will occur if the last dose was well tolerated and after satisfactory review of the available safety and PK data.

Data required for dose escalation evaluation will be determined by cohort and will be based on review of safety and PK data through a minimum of 14 days of dose administration, with at least 7 of these days at the previous target dose level. Each dose escalation will be based on review of available safety and PK data for at least 7 participants from that cohort. Details on safety assessments included in dose escalation review are provided in [Section 8.2](#) and [Appendix 2](#).

The timing of safety and PK required for dose escalation will be provided in writing prior to initiation of dosing for each such cohort.

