To assess the relationship between the PK parameters and dose for PF-07081532, dose normalized AUC₂₄ and C_{max} will be plotted against treatment (using a logarithmic scale) for Day 1, Day 28 (Parts A, B and C), and Day 42 (for Parts B and C only) separately and will include individual participant values and the geometric means for each dose. Geometric means will have a different symbol than the individual values. The values will be dose normalized (to a 1 mg dose) by dividing the individual values and raw geometric means by dose. A footnote will be added to the plots to indicate that geometric means are presented.

The observed accumulation ratio for AUC₂₄ and C_{max} will be analyzed after natural log transformation using a one-way analysis of variance with a single term for dose. The means and 90% confidence intervals (CIs) obtained from the model will be back-transformed to provide means and 90% CIs for the accumulation for each dose.

Supporting data from the estimation of t_{1/2} will be listed where applicable: terminal phase rate constant (k_{el}); goodness of fit statistic from the log-linear regression (r²); and the first,

last, and number of time points used in the estimation of k_{el} . This data may be included in the clinical study report.

[figure not shown]
Presentations for PF-07081532 concentrations will include:

- a listing of all concentrations sorted by participant ID, treatment, and matrix and nominal time postdose. The concentration listing will also include the actual times. Deviations from the nominal time will be given in a separate listing.
- a summary of concentrations by treatment, and nominal time postdose, where the set of statistics will include n, mean, median, standard deviation, coefficient of variation (cv), minimum, maximum and the number of concentrations above the lower limit of quantification.
- median concentrations time plots (on both linear and semi-log scales) against nominal time postdose by (all treatments on the same plot per scale, based on the summary of concentrations by treatment and time postdose), for Day 1, Day 28 and Day 42 (for Parts B & C only).
- mean concentrations time plots (on both linear and semi-log scales) against nominal time postdose by (all treatments on the same plot per scale, based on the summary of concentrations by treatment and time postdose), for Day 1, Day 28 and Day 42 (for Parts B & C only).

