Appendix 3.2. Example SAS Code for Statistical Analyses

Appendix 3.2.1. MMRM for PK analysis:

```
proc mixed data = input_dataset method = reml;  
    class participant dose day;  
    model pk_var = dose day dose*day /ddf = kr residual;  
    repeated day / participant = participant type = un;  
run;
```

CCD

CCI

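### No readable passage plans an estimate with a confidence interval of how AUC24 and Cmax change with dose; a power model on values already derived would supply one cheaply

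*Protocol*

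**What the plan says.** Protocol 9.4.3.1 plots dose-normalised AUC24 and Cmax against dose, with individual values and a geometric mean per dose, and states the purpose: "These plots will be used to help understand the relationship between the PK parameters and dose (and treatment, if applicable". SAP 6.3.1 takes up the same question for these two parameters; its paragraph begins "To assess the relationship between the PK parameters and dose for PF-07081532, dose normalized". It then says that the values "will be plotted against treatment (using a logarithmic scale) for Day 1, Day 28 (Parts A, B and C), and Day 42"; Day 42 applies to Parts B and C. SAP Table 6 adds descriptive statistics by treatment and day, including the geometric mean and geometric CV%.

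Two other PK models are readable in the SAP:
- In SAP 6.3.1 the accumulation ratio "will be analyzed after natural log transformation using a one-way analysis of variance with a single term for dose". This analysis does report an interval for every dose, on the original scale: "The means and 90% confidence intervals (CIs) obtained from the model will be back-transformed".
- SAP Appendix 3.2.1 holds code with the line "model pk_var = dose day dose*day /ddf = kr residual". Dose is a class variable there, no slope or least-squares means are requested, and the readable text of SAP 6.3.1 does not call the code.

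Two escalation rules rest on projected exposure. Under Protocol 6.6.1, if the group mean Cmax or AUC "of the next planned dose is projected to exceed the escalation limits, that dose will not be explored". Protocol 4.3.4 lets dose levels be changed on condition that the projected rise in each exposure measure "between dose levels is no greater than approximately 3.3-fold and the projected exposure is not expected to exceed the PK stopping limits". The readable text does not say how the projection is made. Protocol 9.5 mentions that the unblinded reviews may assist PK modelling.

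**The concern.** The documents pose a quantitative question across doses and answer it group by group. With about 8 active participants per dose, a moderate departure from proportionality is hard to see between neighbouring doses. The secondary objective of characterising plasma PK could then end without a stated degree of proportionality or its uncertainty.

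The slope b on the log-log scale also matters for projection. A 3.33-fold dose step (30 to 100 mg, or 300 to 1000 mg) multiplies exposure by 3.33^b: 2.62 at b = 0.8, 3.33 at b = 1.0 and 4.24 at b = 1.2. A slope modestly above 1 therefore takes such a step past the increment of about 3.3-fold in Protocol 4.3.4. At b = 1.2 the dose-normalised geometric mean rises only 3^0.2 = 1.25-fold from 10 to 30 mg.

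**Working it through.** The readable text states no precision or proportionality figure, so there is none to reproduce.

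**Inputs**
- Doses of 10, 30, 100, 200 and 300 mg: sample targets in Protocol Table 9, marked there as illustrative.
- 8 active participants per Part A cohort, up to 5 cohorts: Protocol 4.1.
- 90% intervals: the level SAP 6.3.1 uses for its PK model.
- Between-participant CV: assumed, 30% to 60%.

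**Formulas**, with one value per active participant and x = ln(dose)
- Residual SD: s = √ln(1 + CV²), which is 0.2936 at 30% and 0.5545 at 60%.
- Half-width of b: t(0.95, N−2) · s / √Sxx, with Sxx = 8 · Σ(x − x̄)² over the doses.
- Factor for the projected geometric mean at dose d: exp{t · s · √(1/N + (ln d − x̄)²/Sxx)}.

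**Slope**

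| Cohorts | N | Sxx | t | Half-width of b, CV 30% to 60% |
|---|---|---|---|---|
| 2 (10, 30 mg) | 16 | 4.83 | 1.761 | 0.235 to 0.445 |
| 3 (to 100 mg) | 24 | 21.22 | 1.717 | 0.109 to 0.207 |
| 5 (to 300 mg) | 40 | 62.81 | 1.686 | 0.062 to 0.118 |

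Example, two cohorts at CV 30%: 1.761 × 0.2936 / √4.83 = 0.235. A simulation with true slope 1 and CV 40% gave 89.8% to 89.9% coverage of the 90% interval for two and for five cohorts.

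**Projection**
- 100 mg after two cohorts: x̄ = 2.852 and ln 100 = 4.605, so the root is √(1/16 + 1.753²/4.83) = 0.836. At CV 30% the factor is exp(1.761 × 0.2936 × 0.836) = 1.54; at CV 60% it is 2.26. With 7 per cohort, the minimum for an escalation review in Protocol 6.6.1, it is 1.60 to 2.42.
- 200 mg after three cohorts: x̄ = 3.436 and ln 200 = 5.298, so the root is √(1/24 + 1.862²/21.22) = 0.453. The factor is 1.26 to 1.54.
- Slope error alone would understate this. After three cohorts it gives only 1.14 to 1.28 over a 3.33-fold step, because it leaves out the error in the fitted mean.

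**Comparison of two neighbouring doses**: the ratio of two geometric means of 8 has limits ×/÷ exp(1.761 · s · √(2/8)) = 1.30 to 1.63. The 1.25-fold rise at b = 1.2 lies inside them.

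**Which values can enter the model**
- In Table 9 every sample cohort receives 10 mg on Day 1, so Day 1 values carry no dose range under that scheme. The slope has to come from the last dose day.
- Protocol 9.4.3.1 summarises by actual dose received. SAP 6.3.1 plots against treatment, and SAP 5.3.3 leaves days on a non-assigned dose out of the summary statistics. The two must be reconciled before the model's data set is defined.
- Protocol 4.3.5 lets participants continue at an individually tolerated dose, so dose may depend on exposure. If high exposure limits tolerability, lower doses collect high-exposure participants and the slope flattens; other selection could steepen it.

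**The case against.** **Escalation does not depend on this slope.** A reader might infer that the plan needs the power-model estimate in order to escalate. It needs a projection, and the PK modelling mentioned in Protocol 9.5 could supply it. No passage makes the plots the escalation tool, and parts of Protocol 4.3 and of the PK analysis text are blacked out. The absence of a projection method cannot be concluded. This objection stands.

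**The relationship is not left to visual judgement alone.** SAP Table 6 gives N, geometric mean and geometric CV% for each group, from which an interval per dose or for a ratio of doses can be worked out. This stands too. What remains is that no readable analysis reports such an interval or combines the doses.

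**Much of the apparent gain is dose range, not method.** It is tempting to contrast a weak two-dose comparison with a strong five-cohort slope. With a true slope of 1.2, comparing 10 with 300 mg alone (8 each) excludes proportionality in 100%, 96% and 75% of trials at CV 30%, 40% and 60%; the five-cohort model does so in 100%, 99% and 88%. The plots show all doses, so a fair contrast is modest.

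**The gain is least at the first escalations.** With two doses the slope is the two-group comparison rescaled by the log dose ratio. A true slope of 1.2 is then detected in 41% down to 19% of trials.

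**The setting is Phase 1.** Protocol 9.1 plans no hypothesis tests, and the readable sample size rationale in 9.2 is not a precision calculation. That makes this an improvement and not a defect, but it does not rule out an estimate with an interval; SAP 6.3.1 already reports one for accumulation.

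**Conclusion.** The point holds as a low-cost improvement. In the readable text, both documents ask how AUC24 and Cmax relate to dose and answer with plots and per-group summaries, without an estimate and CI across doses. Under the stated assumptions the five-cohort slope would be informative and the two-cohort slope would not separate 1.0 from 1.2. The intervals scale with the assumed CV and would change with the doses actually given, since Table 9 is only a sample. Redacted text could hold further analyses. The documents do not support the stronger readings that escalation depends on this estimate or that the relationship is judged from the plots alone.

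**What to change.** Keep the plots and add to SAP 6.3.1:
- **Model.** ln(parameter) = a + b · ln(dose) for AUC24 and Cmax, fitted to last-dose-day values: Day 28 in Part A, and Day 42 in Parts B and C separately, or pooled only with a Part/population term. Add a formulation term if tablets are used.
- **Report.** b and the fitted geometric means, each with a 90% CI.
- **Dose.** Actual dose received for the main fit, in line with Protocol 9.4.3.1. Repeat it in participants at their assigned dose only, in line with SAP 5.3.3. State that tolerability-limited dosing can bias the slope in either direction. The second fit shows how sensitive the slope is to these participants; it does not remove the selection.
- **Projection.** State how exposure at the next dose is projected for Protocol 6.6.1. If this fit is used in support, give the full interval of the projected geometric mean, and do not let it replace other PK modelling at early escalations.

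The cost is SAP wording and two short regressions per parameter in each Part, on values already derived. Protocol section 9 lets the SAP modify the outlined analyses and reserves amendments for major changes to the primary endpoints or their analyses, so this secondary PK analysis can be added in the SAP. The downsides are a log-linear assumption, which the existing plots check, and the possible selection bias above.
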